## 3 Study Design

### 3.1 Characteristics

This is a Phase 2, single arm, open-label, multicenter study evaluating the feasibility of a treatment regimen comprised of nivolumab administered approximately every 2 weeks before and during chemoradiation and as an adjuvant therapy for 3 months to patients with stage II-IVB NPC who are planning to undergo chemoradiation treatment of their cancer.

A run-in phase will precede expansion, to establish basic feasibility of the nivolumab schedule. The run-in cohorts will include 6 patients at each dose schedule, with 2 planned changes in dose schedule if >33% toxicity or other DLT is observed. A minimum of 6 patients and maximum of 18 patients may be enrolled in the three run-in cohorts. The MTD schedule will be selected when 4/6 patients at a dose schedule complete therapy without grade 3-4 immune related toxicity. All patients will receive the same dose of nivolumab (240mg).

At the starting dose schedule, patients will receive nivolumab for 1 cycle prior to initiation of chemoradiation (approximately 14 days). Patients will subsequently continue with nivolumab every 14 days until completion of chemoradiation. In dose schedule 2, patients will start nivolumab concurrent with start of chemoradiation. In dose schedule 3, patients will start nivolumab after completion of chemoradiation (adjuvant nivolumab only).

DLT criteria are grade  $\geq 3$  immune-related adverse events, need to hold nivolumab for >28 days due to toxicity, and for patients receiving concurrent nivolumab with chemoradiation, inability to complete chemoradiation or need to hold chemoradiation for >3 days due to immune-related

toxicity.

The expansion phase will continue after the run-in phase has been used to establish the MTD schedule for nivolumab. The expansion phase will be powered to test the feasibility of completion of the program as compared to the current standard of care.

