### 3.4 Number of Subjects

A maximum of 40 evaluable patients will be enrolled in the study using a Simon's two-stage design for the primary endpoint. Patients who are enrolled at the maximally tolerated dose of

nivolumab during the run-in phase will be included in the determination of the primary endpoint. Non-evaluable patients will be replaced per the replacement policy (see section 8.2.5). For the primary endpoint, this design yields a type I error rate of 0.05 and power of 80% if the true rate of completion of adjuvant therapy is 0.7.

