## 8.2 Determination of Sample Size and Accrual Rate

### 8.2.1 Sample Size and Power Estimate

We expect the true completion rate of this combined chemoradiation-nivolumab regimen followed by adjuvant nivolumab to be 70%, versus the null hypothesis of 50% (the rate of completion of a standard adjuvant cisplatin-based platform is 52%).

Simon's two-stage design will be used to test this endpoint. In the first stage, 22 patients will be accrued. If 11 or fewer completions, the study will be stopped. Otherwise, 18 additional patients will be accrued for a total of 40 participants.. The null hypothesis will be rejected if 26 or more completions are observed in 40 patients. This design yields a type I error rate of 0.05 and power of 80% when the true completion rate is 0.7.

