### **8.2.3 Expansion phase**

Sample size for the expansion cohort will be a minimum of 9 patients and a maximum of 22 patients (Simon's two-stage design, see statistical plan).

The 6 patients treated at the final dose from the run-in cohort will be included in statistical comparisons. This would yield a minimum total sample size of 15 patients, and a maximum sample size of 28 patients treated at the MTD schedule across the run-in and expansion phases, assuming 6 patients treated at the MTD schedule in the run-in and 22 patients treated at MTD schedule in the expansion cohort.)

The rate of completion of all adjuvant therapy by patients treated at the MTD schedule will be determined and compared to a historical control rate of 52%.

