### **8.2.4 Statistical plan**

Simon's two-stage design will be used to test the primary endpoint for the phase II study. The null hypothesis that the completion rate is 0.5 will be tested against a one-sided alternative 0.7. In the first stage, 15 patients will be accrued (including 6 patients at MTD schedule from the run-in phase). If there are 7 or fewer completions in these 15 patients, the study will be stopped. Otherwise, 13 additional patients will be accrued for a total of 28 patients accrued in the expansion phase. The null hypothesis will be rejected if 18 or more completions are observed in 28 patients. This design yields a type I error rate of 0.09 and power of 80% when the true completion rate is 0.7.

We propose that the final decision about the direction of future strategy and additional expansion studies should be made based on careful analysis of subpopulations with particular attention to feasibility, toxicity, and observed immunodulatory responses.

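### The six run-in patients count in the primary completion test after a 4-of-6 gate, but the stated type I error and power are plain two-stage figures not established for the combined run-in and test

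*Combined protocol and SAP*

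**What the plan says.** **The gate.** Section 3.1 has "The MTD schedule will be selected when 4/6 patients at a dose schedule complete therapy without grade 3-4 immune related toxicity". Sections 3.3 and 8.2.2 describe the gate differently. Schedules 1 and 2 are judged on high-grade immune toxicity or another DLT while nivolumab is given with chemoradiation, and schedule 3 is judged during the adjuvant phase. Three or more failures among six move the run-in to the next schedule, or end the study at schedule 3. Up to three cohorts of six are possible.

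**The reuse.** Section 3.4 says of patients on the maximally tolerated dose of "nivolumab during the run-in phase will be included in the determination of the primary endpoint". Section 8.2.3 adds: "The 6 patients treated at the final dose from the run-in cohort will be included in statistical comparisons".

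**The test.** Section 8.2.1 sets the null completion rate at 50%. "In the first stage, 22 patients will be accrued. If 11 or fewer completions, the study will be stopped". Eighteen more patients follow otherwise, and "The null hypothesis will be rejected if 26 or more completions are observed in 40 patients". Section 8.2.4 makes the test one-sided.

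**The stated performance.** "This design yields a type I error rate of 0.05 and power of 80% when the true completion rate is 0.7" (8.2.1, with the same figures in 3.4 and the abstract). No section allows for the run-in gate.

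**The concern.** A schedule reaches the primary test only if its first six patients did well enough, and those six are then counted as if they had been sampled without regard to outcome. If run-in success is related to completion, they bring an inflated completion count into stage 1. The false-positive rate given a passed run-in rises, the futility stop weakens and the reported completion rate is too high.

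The two outcomes are related by the protocol's own rules. A nivolumab hold of more than 28 days is a DLT and also a ground for stopping nivolumab. Several grade 3 and most grade 4 immune events in 5.2.1 take the patient off protocol therapy. Such a patient cannot complete six adjuvant cycles. The trial's one formal claim is that a completion rate exceeds a historical one, so the stated error rates should be those of the procedure that will actually be run.

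**Working it through.** **Inputs from the documents.** Null rate 0.50, alternative 0.70, stop at 11 or fewer of 22, reject at 26 or more of 40 (8.2.1); one-sided (8.2.4); six run-in patients counted (8.2.3); gate of at least 4 of 6, up to three cohorts (3.1, 3.3, 8.2.2). The six are placed inside stage 1. Section 8.2.4 says this for its own 15/28 design, and it is assumed here for 22/40.

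**Step 1: the plan's own figure.** For unselected patients,

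P(reject) = Σ over s = 12 to 22 of P[Bin(22, p) = s] × P[Bin(18, p) ≥ 26 − s].

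This gives 0.0396 at p = 0.50 and 0.8028 at p = 0.70. The 80% is reproduced, and 0.05 is a ceiling with some slack.

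**Step 2: add the gate.** Assumptions: each patient completes with probability p, a non-completer is a run-in failure with probability r, and a completer never is. The documents give no value for r, so a range is used. Let X ~ Bin(6, p) be completers among the six, Y ~ Bin(16, p) completers in the rest of stage 1, and Z ~ Bin(18, p) completers in stage 2.

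- P(pass) = Σ over x of P(X = x) × P[Bin(6 − x, r) ≤ 2].
- Reject if the run-in passes, X + Y ≥ 12 and X + Y + Z ≥ 26.
- Error or power given a pass = P(pass and reject) / P(pass).
- Over three schedules with the same p: P(pass and reject) × (1 + f + f²), where f = 1 − P(pass).

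**Step 3: worked case, r = 1.**

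- At p = 0.50, P(pass) = (15 + 6 + 1)/64 = 0.3438 and P(pass and reject) = 0.0278.
- Given a pass the error is 0.0278/0.3438 = 0.081. Over three schedules it is 0.0278 × (1 + 0.6562 + 0.6562²) = 0.058.
- Expected completers among the six, given a pass, are (4×15 + 5×6 + 6×1)/22 = 4.36 instead of 3.0. The shift in a 40-patient rate is 1.36/40 = 3.4 percentage points.
- At p = 0.70, P(pass) = 0.7443 and P(pass and reject) = 0.6403. Power is 0.6403/0.7443 = 0.860 given a pass and 0.846 over three schedules. Expected completers are 4.72 instead of 4.2, a shift of 0.52/40 = 1.3 points.

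**Step 4: the range.**

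| | no gate | r = 0.5 | r = 0.75 | r = 1 |
|---|---|---|---|---|
| Type I error at 50%, given a pass | 0.040 | 0.045 | 0.056 | 0.081 |
| Type I error at 50%, three schedules | – | 0.045 | 0.053 | 0.058 |
| Stage-1 stop probability at 50%, given a pass | 0.58 | 0.54 | 0.47 | 0.34 |
| Power at 70%, given a pass | 0.803 | 0.814 | 0.832 | 0.860 |
| Power at 70%, three schedules | – | 0.813 | 0.830 | 0.846 |
| First schedule kept and declared feasible, at 70% | – | 0.775 | 0.72 | 0.64 |

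Given a pass, the error is 0.049 at r = 0.60 and first exceeds 0.05 near r = 0.65.

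**Step 5: no association.** If DLT-free status is independent of completion, the error given a pass stays at 0.0396. The gate then acts only as an extra stop. With an assumed DLT-free probability of 0.70, overall power at 70% is 0.789.

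**The case against.** A reader might infer that 0.05 and 80% simply fail. The documents do not support that, for three reasons.

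**The gate is not the endpoint.** Read literally, 3.1 selects on completing therapy, which corresponds to r = 1. Sections 3.3 and 8.2.2 judge schedules 1 and 2 on DLT during the concurrent phase, whereas 8.4.2 defines the endpoint as completing all post-chemoradiation cycles. Adjuvant-phase progression, toxicity or withdrawal then cannot affect the gate. The link is also partial. The general table in 5.2.1 lets some grade 3 patients resume, and a chemoradiation hold of more than 3 days for immune toxicity is a DLT that does not in itself end nivolumab.

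**Nothing in the documents points to a high r.** The only head and neck nivolumab toxicity rate given is 13.1% grade 3/4, in the phase 3 trial of previously treated disease (1.2.3.1). If that were the run-in failure rate here, which is an assumption, r at p = 0.50 would be 0.131/0.50 = 0.26. The error given a pass would be 0.041 and three-schedule power 0.805.

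**Power is not lost in this model.** Setting 0.775 / 0.72 / 0.64 against 80% counts only the first schedule. A failed run-in restarts at the next schedule, and with all three at 70% power is 0.81 to 0.85.

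All three arguments stand, and they limit the size of the problem. They do not remove it: the six patients are reused after an outcome-dependent gate, schedule 3 is gated in the adjuvant phase itself, and the plan states error rates for a different procedure.

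**Conclusion.** The concern holds as a gap in the stated operating characteristics, of modest and uncertain size. The figures in 8.2.1, 3.4 and the abstract describe unselected patients and are not established for the run-in plus test.

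With r up to about 0.6 the type I error stays within 0.05 on both readings. Above about 0.65 it exceeds 0.05 given a pass, with upper bounds at r = 1 of 0.081 given a pass and 0.058 over three schedules. Given a pass, the futility stop weakens and the completion rate is biased upward, by at most about 3.4 percentage points at a true rate of 50%. Only the chance that the first schedule itself is kept and declared feasible falls clearly below 80%.

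These results rest on the 22/40 rule, on the six sitting in stage 1, on a common completion rate across schedules, and on the assumed r. The different 15/28 design in 8.2.3 and 8.2.4 is a separate inconsistency and is not used to enlarge this point.

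**What to change.** 1. In 8.2.1, 3.4 and the abstract, state the type I error, early-stop probability and power of the combined run-in and two-stage procedure, both given a passed run-in and over the three schedules, for a stated range of association between DLT and completion.
2. In 8.4.2, prespecify a sensitivity analysis giving the completion rate with an exact confidence interval for the patients enrolled after the run-in decision: 40 − 6 = 34, or 22 − 6 = 16 if the study stops at stage 1.
3. Reconcile the selection wording of 3.1 with 3.3 and 8.2.2, since the size of the effect depends on which outcome forms the gate.

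The cost is a short exact calculation and some wording, with no extra patients. The stated figures may look slightly less favourable, and the sensitivity interval will be wider than the primary one. The six patients can stay in the primary analysis. No change of cutoff is required, and neither is a p-value conditional on passing the run-in, which would need the unknown association as an input.

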### 3.2 Study Schema

#### On-treatment schema (Dose Schedule 1):

		Adjuvant Phase																							
Cycle #	1	2	3		4		5		6		7		8		9		10		11		12				
Week #	1	2	3	4	5	6	7	8	9	10	11	12	13	14	15	16	17	18	19	20	21	22	23		
Cisplatin		C	C	C	C	C	C	C																	
Radiation		X	X	X	X	X	X	X																	
Nivolumab	N	N	N		N	N							N		N		N		N		N		N		

Nivolumab schedule (starting dose schedule): Priming and concurrent nivolumab will be given in conjunction with chemoradiation. Patients will receive 1 cycle of priming nivolumab on C1D1, and 14 days later, start weekly cisplatin 40 mg/m^2, IV, concurrent with 33-35 fractions (6.5-7 weeks) of RT, with concurrent cycles 2-5 of nivolumab every 14 days. No nivolumab will be given on C6D1, to allow for recovery from toxicities. At C7D1, patients will initiate adjuvant nivolumab, every 14 days for cycles 7-12. Immune-related toxicities should be at grade 1 or lower prior to starting a patient on the adjuvant phase of therapy; if not, initiation of the adjuvant phase should be delayed until resolution of toxicities.

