Study Design	
 
This is a phase II multi-institution, single-arm, open label clinical trial of concurrent and adjuvant nivolumab in Stage II-IVB endemic-type nasopharyngeal carcinoma patients who plan to undergo chemoradiation therapy for treatment of their cancer.
 
A run-in phase will precede expansion, to establish basic feasibility of the nivolumab schedule. The run-in cohorts will include 6 patients at each dose schedule, with 2 planned changes to the dose schedule if >33% toxicity or other dose limiting toxicity (DLT) is observed. A minimum of 6 patients and maximum of 18 patients may be enrolled in the run-in phase.
 
A total maximum of 40 evaluable patients will be enrolled for the primary endpoint. This design yields a type I error rate of 0.05 and power of 80% if the true rate of completion of adjuvant therapy is 0.7.
 
At the starting dose schedule, patients will receive nivolumab for 1 cycle prior to initiation of chemoradiation (approximately 14 days). Patients will subsequently continue with nivolumab every 14 days until completion of chemoradiation. If a dose schedule shows >33% toxicity or other DLT, then subsequently enrolled patients will be treated at the next dose schedule. In dose schedule 2, patients will start nivolumab concurrent with start of chemoradiation. In dose schedule 3, patients will start nivolumab after completion of chemoradiation (adjuvant nivolumab only). All patients will receive the same dose of nivolumab (240mg).
 
DLT criteria are grade <math>\geq</math>3 immune-related adverse events, need to hold nivolumab for >28 days due to toxicity, and for patients receiving concurrent nivolumab with chemoradiation, inability to complete chemoradiation or need to hold chemoradiation for >3 days due to immune-related toxicity.
 
Adjuvant therapy with nivolumab for 6 cycles will start at 4 weeks following completion of chemoradiation, or when immune-related toxicities are at grade 1 or lower, whichever comes later.
 
Patients will be followed for overall response rate, locoregional control and distant metastasis rates, and overall survival rate for 1 year after end of treatment.
 

Number of patients	A maximum of 40 evaluable patients will be enrolled in the study using a Simon's two-stage design for the primary endpoint. Non-evaluable patients will be replaced per the replacement policy.

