### **Dosing Delays for General and Immune-Related Adverse Events**

Algorithms in tables which follow and Appendix 5 should be consulted for specific immune-related AEs and followed preferentially rather than this general guideline.

Grade of Event	Management/Next Dose for Nivolumab
≤ Grade 1	No change in dose
Grade 2	Hold until ≤ Grade 1 Resume at same dose schedule when toxicity ≤ Grade 1
Grade 3	Hold* until ≤ Grade 2 Resume at same dose schedule when toxicity ≤ Grade 2
Grade 4	Off protocol therapy

\*Patients requiring a delay of > 28 days should go off protocol therapy

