**Criteria to Resume Nivolumab**

Patients may resume treatment with nivolumab when the drug-related AE(s) resolve to the grade specified in the tables above and as detailed in Appendix 5.

If the criteria to resume treatment are met, the patient should restart treatment at the next scheduled time point (two-week interval) per the protocol.

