**Discontinuation Criteria**

Treatment with nivolumab should be permanently discontinued as specified in the tables above and guidelines for management in Appendix 5. Additional criteria for discontinuation include:

- Any Grade 2 drug-related uveitis or eye pain or blurred vision that does not respond to topical therapy and does not improve to Grade 1 severity within the re-treatment period OR requires systemic treatment;
- Grade 3 drug-related uveitis, pneumonitis, bronchospasm, diarrhea, colitis, neurologic adverse event, hypersensitivity reaction, or infusion reaction of any duration requires discontinuation;
- Grade 3 drug-related thrombocytopenia > 7 days or associated with bleeding requires discontinuation;
- Any Grade 4 drug-related adverse event or laboratory abnormality, with the exception of those noted below:
  - Isolated Grade 4 amylase or lipase abnormalities that are not associated with symptoms or clinical manifestations of pancreatitis and decrease to < Grade 4 within 1 week of onset;
  - Isolated Grade 4 electrolyte imbalances/abnormalities that are not associated with clinical sequelae and are corrected with supplementation/appropriate management within 72 hours of their onset.
  - Any grade 3 or 4 drug-related laboratory abnormality or electrolyte abnormality not associated with underlying organ pathology that does not require treatment except for electrolyte replacement OR hormone/steroid replacement **does not** require treatment discontinuation.
- Any adverse event, laboratory abnormality, or intercurrent illness which, in the judgment of the Investigator, presents a substantial clinical risk to the patient with continued nivolumab dosing;
- A delay in nivolumab treatment of 28 days.

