a Each 14-day period of treatment will represent 1 cycle and begins from C1D1.b Baseline conditions assessmentc As part of efficacy assessments, quality of life by FACT-NP, FACT-Taxane, HHIE-S, and EuroQOL EQ-5D will be administered at baseline, at cycle 6, at end of treatment and at all followup visits. Survey's not available in the patient's language may be administered by the study staff in an interview format with a translator, however failure to obtain any individual quality of life survey not available in the patient's language will not be considered a protocol deviation.d Toxicity will be assessed by CTCAE v5.0f There is a 72 hour window of scheduled nivolumab administration. **In Dose Schedule 1:** Nivolumab will be administered on C1D1 for priming and then q14 days beginning C2D1, concurrent with chemoradiation, until C5D1. Nivolumab will not be administered on C6D1 to allow for any resolution of toxicities. Beginning C7D1, adjuvant nivolumab q14 days will be administered until C12D1. **In Dose Schedule 2:** Nivolumab will be administered on C1D1 concurrent with chemoradiation (no priming), and then q14 days until C4D1. Nivolumab will not be administered on C5D1 to allow for any resolution of toxicities. Beginning C6D1, adjuvant nivolumab q14 days will be administered until C11D1. **In Dose Schedule 3:** Nivolumab will not be administered until after completion of chemoradiation. Beginning C6D1, adjuvant nivolumab q14 days will be administered until C11D1. Immune-related toxicities should be at grade 1 or lower prior to starting a patient on the adjuvant phase of therapy; if not, initiation of the adjuvant phase should be delayed until resolution of toxicities.h Physical Exam includes weight measurementsi Disease-specific criteria (for CRF purposes, e.g.: GU assessment, BR disease Eval, AML-MDS Summary, etc.)j Measurable disease will be assessed using RECIST 1.1 criteriak For the **baseline** tissue collection, if a biopsy was performed within 90 days prior to C1D1, and no intervening treatment was given, a repeat biopsy is not required if adequate tumor tissue can be provided. **Repeat biopsy** will be at the discretion of the investigator, and timing will depend on Dose Schedule. **In Dose Schedule 1:** Tumor tissue post-nivolumab during cycle 1 AND after first week of radiation therapy. **In Dose Schedule 2 and 3:** Tumor tissue after first week of radiation therapy only. See appendix 4 for further details.l All blood draws may be completed within 7 days prior to start of therapy unless otherwise specified; screening labs must be completed within 14 days of Cycle 1 Day 1.m Hemoglobin, hematocrit, platelets, total white blood cell count (WBC) and differentialn Alkaline phosphatase, aspartate aminotransferase/alanine aminotransferase (ALT/AST), total bilirubin, total protein, albumin, calcium, phosphorus, magnesium, blood urea nitrogen (BUN), creatinine, glucose fasting), potassium, sodium, chloride, bicarbonate, uric acid, LDH, fasting lipid panel (LDL, total cholesterol, triglycerides), thyroid stimulating hormone (TSH).o **Pre-menopausal females:** serum or urine pregnancy test within 7 days prior to start of study drug. Serum pregnancy test by local laboratory  $\leq$  1 day prior to C1D1 for women of childbearing potential. If the serum pregnancy test results are not available on C1D1, a urine pregnancy test can be performed on C1D1 to confirm that the patient is not pregnant prior to dosing.p See Appendix 4 for details on tissue specimen collection and processing.q Collection of peripheral blood for correlative biomarkers and peripheral immune changes must be collected with every cycle of nivolumab. Blood will also be collected in post-treatment followup to 1 year.r Imaging with MRI nasopharynx/face/neck and whole body PET-CT will be performed at screening and at end of treatment and at 1 year followup, with further imaging to be performed as clinically indicated.

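### A last concurrent nivolumab dose held for a short toxicity runs into the planned no-nivolumab cycle, and the plan's 28-day rules then disagree on whether the patient may enter the adjuvant phase

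*Combined protocol and SAP*

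**What the plan says.** **Schedule.** Table 6.1 fixes the calendar: "Each 14-day period of treatment will represent 1 cycle and begins from C1D1". Under Dose Schedule 1 (section 3.2), nivolumab is given on C1D1 and then with chemoradiation through C5D1. After that, "No nivolumab will be given on C6D1, to allow for recovery from toxicities", and "At C7D1, patients will initiate adjuvant nivolumab, every 14 days for cycles 7-12". For Dose Schedule 2, Table 6.1 puts the last concurrent dose at C4D1, no dose at C5D1 and the first adjuvant dose at C6D1. The Schedule 2 text in 3.2 is itself inconsistent: it lists concurrent cycles 2 to 5 but omits C5D1. I use Table 6.1. Schedule 3 has no concurrent nivolumab and is not affected.

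**Restart after a hold.** Section 5.2.1 (Criteria to Resume Nivolumab): "the patient should restart treatment at the next scheduled time point (two-week interval) per the protocol". Doses have a 72-hour window (6.1.2.1, Table 6.1).

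**Limits on delay, all in 5.2.1.**
- Discontinuation Criteria, under permanent discontinuation: "A delay in nivolumab treatment of 28 days". The line has no qualifier.
- Footnote to the general dose-delay table: "Patients requiring a delay of > 28 days should go off protocol therapy".
- Opening text: more than 28 consecutive days because of toxicity ends protocol therapy, unless the Principal Investigator and investigators agree to go on.

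**Adjuvant start.** Abstract: "Adjuvant therapy with nivolumab for 6 cycles will start at 4 weeks following completion of chemoradiation", or later if immune-related toxicity has not yet settled to grade 1. Section 3.2 and Table 6.1 give a cycle number instead, and also let the start wait for toxicity to resolve. The abstract allows the 23-week course to stretch to 33 weeks for that reason.

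**Endpoint.** Completion means all post-chemoradiation nivolumab cycles (8.4.2). Patients given at least one cycle at the selected schedule are analysed (8.4.1). Only patients who drop out before any nivolumab are replaced (8.2.5).

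**The concern.** The cycle left free for recovery sits directly after the last concurrent dose. A hold at that dose cannot end at the next two-week point, because that point is the omitted one. It runs on to the first adjuvant dose, however quickly the toxicity clears. A similar hold at any other concurrent dose costs 14 days.

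The trigger need not be severe. Section 5.2.1 calls for a hold for most grade 2 events, and for grade 1 pneumonitis, fever and amylase or lipase elevation. No passage says whether the planned no-nivolumab cycle counts towards the 28 days.

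At stake is the primary endpoint. A patient stopped at this point has received study drug, so is not replaced, stays in the analysis and cannot complete six adjuvant cycles. Two sites could follow different sentences of the same section and classify identical patients in opposite ways.

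**Working it through.** **1. Calendar.** Day of cycle c = 1 + 14 × (c − 1). This gives C4D1 = 43, C5D1 = 57, C6D1 = 71, C7D1 = 85 and C12D1 = 155. Day 155 is in week 23, which reproduces the abstract's 23-week course.

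**2. Gap on the schema.**
- Schedule 1: last concurrent dose held on day 57, next permitted dose on day 85: 85 − 57 = 28 days.
- Schedule 2 (Table 6.1): C4D1 on day 43 to C6D1 on day 71: 71 − 43 = 28 days.
- With the restart visit moved by up to 3 days either way: 25 to 31 days.
- A hold of up to 72 hours fits the dosing window and creates no gap.

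**3. Gap under the abstract's start.** I assume radiation starts on a Monday (day 15 in Schedule 1, day 1 in Schedule 2), with five fractions a week and no breaks.
- Schedule 1: 33 fractions end on day 15 + 42 + 2 = 59, and 35 fractions on day 15 + 42 + 4 = 61. Adding 28 gives day 87 to 89, so the gap is 30 to 32 days.
- Schedule 2: radiation ends on day 45 to 47. Adding 28 gives day 73 to 75, so the gap is again 30 to 32 days.

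**4. What is being counted.** Counting from the last dose given cannot be intended: a patient with no toxicity already has 28 days between C5D1 and C7D1. With C5D1 held, that count would be 85 − 43 = 42 days. Two counts remain, both from the held date:

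| Count from held date | Days | Discontinuation Criteria (28) | Table footnote (>28) | 5.2.1 opening text (>28, due to toxicity, unless agreed) |
|---|---|---|---|---|
| To C7D1, planned cycle included | 28 | met | not met | not met |
| To the abstract's start, planned cycle included | 30–32 | met | exceeded by day count | exceeded by day count; cause and agreement still to be judged |
| To C7D1, planned cycle excluded (28 − 14) | 14 | not met | not met | not met |

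**5. Link to the endpoint.** The design in 8.2.1 stops at 11 or fewer of 22 and rejects at 26 or more of 40. Power = Σ P(X₁ = x) × P(X₂ ≥ 26 − x) over x = 12 to 22, with X₁ ~ Bin(22, p) and X₂ ~ Bin(18, p). At p = 0.70 this is 0.803, which reproduces the stated 80%. At p = 0.50 it is 0.040, within the stated 0.05.

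The documents do not say how often this dose would be held. If a share h of would-be completers were lost, p = 0.70 × (1 − h):

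| h (assumed) | p | Power |
|---|---|---|
| 2.5% | 0.6825 | 0.728 |
| 5% | 0.665 | 0.644 |
| 10% | 0.63 | 0.462 |

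Section 8.2.4 still describes a 28-patient design (stop at 7 of 15, reject at 18 of 28). There, h = 5% takes power from 0.801 to 0.670.

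**The case against.** The best reply is that the plan foresaw delay at this transition. The abstract, 3.2 and Table 6.1 all let the adjuvant start wait for toxicity to settle. The course may run 33 − 23 = 10 weeks longer, and 5.2.1 allows continuation by agreement. A patient whose event clears in days has missed one concurrent dose and takes C7D1 on its due date; the table footnote speaks of patients who need a long delay, and this one does not. On the schema the gap is exactly 28 days, so only one of the three limits is reached. If that limit also read as more than 28 days, a restart on the nominal day would trigger nothing.

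Much of this stands. A reader might infer that the plan as a whole ends nivolumab for such patients. It does not, because only the Discontinuation Criteria do so at 28 days and other provisions point the other way. But those provisions do not override that line, which carries no exception. They conflict with it. Changing 28 to more than 28 would still leave a restart late in the window (up to 31 days) and the abstract's start (30 to 32 days) over the limit by day count.

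A reader might also infer that the gap counts as a dose-limiting toxicity in the run-in. The documents do not support that. The criterion is "need to hold nivolumab for >28 days due to toxicity", and after a brief toxicity most of the gap is planned. For Schedules 1 and 2, sections 3.3 and 8.2.2 base the schedule change on toxicity during concurrent treatment. Day 28 of the gap falls on day 85 (Schedule 1) or day 71 (Schedule 2), after radiation has ended on day 59 to 61 or day 45 to 47.

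Finally, the expected 70% completion may already allow for patients stopped under the protocol's own rules, so subtracting them again could double-count.

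**Conclusion.** The concern holds as a conflict between stated rules. In Schedule 1, and in Schedule 2 as Table 6.1 gives it, holding the last concurrent dose beyond 72 hours leads to a restart 28 days later on the schema (25 to 31 with the window) or 30 to 32 days later under the abstract. For that patient one rule requires a permanent stop, others do not, and nothing says whether the planned cycle counts. Completion on the primary endpoint can therefore depend on which sentence a site applies.

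The day counts rest on 14-day cycles and, for the 30 to 32 days, on unbroken radiation starting on a Monday. The effect on the trial cannot be sized from the documents. The fall in power from 0.80 to 0.64 assumes that 5% of would-be completers are affected, that all of them are stopped and that the 70% did not already include them. It shows how sensitive the design is and is not an estimate.

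**What to change.** Reconcile the three 28-day statements in 5.2.1 with each other, with the two descriptions of the adjuvant start (abstract against 3.2 and Table 6.1) and with the planned no-nivolumab cycle. State one way of counting a nivolumab delay: when it begins, when it ends, and whether the planned cycle is included when the hold starts at the last concurrent dose. Refer to that count from 8.4.2, so that discontinuation and classification as a completer follow the same rule. Correct the Schedule 2 cycle numbers in 3.2 at the same time. Which rule to adopt is for the sponsor to decide.

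The cost is amendment wording: a sentence or two in 5.2.1, cross-references, and a note to sites. The sample size and visit schedule need not change unless the sponsor's chosen adjuvant start alters the calendar.
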